14.3.1 Pharmacokinetic Analyses

14.3.1.1 Descriptive Statistics

The TRA (whole blood, plasma, urine, feces, and if applicable emesis), CT1812 and M6 metabolite concentrations (plasma), and PK parameters listed in [Sections 13.3.2, 13.3.5](#) and [13.3.7](#) will be summarized using appropriate descriptive statistics which will be fully outlined in the SAP.

14.3.1.2 Mass Balance

Total radioactivity recovery and the percent of the radioactive dose excreted in the urine and feces will be assessed. Mass balance will be calculated as a sum of the percent of the TRA recovered in urine and feces relative to the administered radioactive dose minus any radioactive dose lost due to emesis (if any occurred).

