Dosage, Dosage Form, Route, and Dose Regimen:	
Study drug will be supplied as capsules of nonradiolabeled CT1812 (powder) and capsules of radiolabeled [¹⁴C]-CT1812 (powder/suspension).
 
The study treatment will consist of 3 capsules: 2 capsules containing CT1812 [REDACTED] and 1 capsule containing ~1 µCi [¹⁴C]-CT1812 ([REDACTED]®).
 
Capsules will be administered orally under fasting conditions on Day 1 at Hour 0 with approximately 240 mL of water. Additional water, up to 50 mL, is permissible to facilitate swallowing multiple capsules.

Key Assessments:	
Mass Balance
 
TRA recovery and the percent of the radioactive dose excreted in the urine and feces will be assessed. Mass balance will be calculated as a sum of the percent of the TRA recovered in urine and feces relative to the administered radioactive dose minus any radioactive dose lost due to emesis (if any occurred).
 
Pharmacokinetics:
 
The following PK assessments will be evaluated, as appropriate:
 
• TRA concentration equivalents are [REDACTED]• TRA concentration equivalents are [REDACTED]

CONFIDENTIAL

CT1812, CA35306, Final Protocol, Amendment 1_15Dec2021

- TRA concentration equivalents [REDACTED]
- CT1218 and M6 concentrations in plasma [REDACTED]
- Ratio of plasma CT1812 to TRA fo [REDACTED].

Metabolite profiling:

CT1812 metabolite profiling will be performed on plasma, urine, and fecal samples. The percent of dose represented by each of the metabolites, if any, will be calculated using the radioactive concentration equivalent data combined with the metabolite profiling data. The percentage of each identified metabolite, if any, to TRA in the plasma will be estimated based on plasma metabolite profiling data. Metabolites accounting for more than 10% of circulating TRA will be identified.

Whole blood to plasma partitioning ratio:

The percentage of TRA in whole blood relative to plasma will be estimated at each time-matched determination of TRA in whole blood and plasma.

Safety:

Safety will be monitored through AEs, 12-lead electrocardiograms (ECGs), vital sign measurements, clinical laboratory tests, physical examinations, ophthalmic examinations, and Columbia-Suicide Severity Rating Scale (C-SSRS). AEs will be tabulated and summary statistics for the 12-lead ECGs, vital signs, and clinical laboratory tests may be computed and provided, as deemed clinically appropriate.

CONFIDENTIAL

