13.3 Pharmacokinetic Assessments

13.3.1 Blood Sampling and Processing

Blood samples for the determination of TRA in whole blood and plasma, CT1812 and M6 concentrations in plasma, and metabolite profiling in plasma will be collected at scheduled time points as delineated in the Study Events Flow Chart ([Section 6](#)).

Predose samples should be handled, processed, analyzed, and stored separately away from the postdose samples to avoid cross contamination.

Instruction for blood sampling, collection, processing, and sample shipment will be provided separately.

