13.3.2 Pharmacokinetic Parameters

PK parameters for whole blood and plasma TRA concentration equivalents and for plasma CT1812 and metabolite M6, will be calculated, as appropriate:

AUC0-t:	The area under the concentration versus time curve, from time 0 to the time of the last common time point “t”, where t is the last common time point at which plasma TRA and plasma CT1812 are quantifiable in all subjects.
AUC0-24:	The area under the concentration versus time curve, from time 0 to the 24-hour time point.
AUC0-last:	The area under the concentration-time curve, from time 0 to the last observed non-zero concentration, as calculated by the linear trapezoidal method.
AUC0-inf:	The area under the concentration-time curve from time 0 extrapolated to infinity. AUC0-inf is calculated as the sum of AUC0-last plus the ratio of the last measurable concentration to the elimination rate constant.
AUC%extrap:	Percent of AUC0-inf extrapolated, represented as $(1 - AUC0\text{-last}/AUC0\text{-inf}) \times 100$.
Cmax:	Maximum observed concentration.
Tmax:	Time to reach Cmax. If the maximum value occurs at more than one time point, Tmax is defined as the first time point with this value.
Kel:	Apparent first-order terminal elimination rate constant calculated from a semi-log plot of the concentration versus time curve. The parameter will be calculated by linear least-squares regression analysis using the maximum number of points in the terminal log-linear phase (e.g., three or more non-zero concentrations).

t½:	Apparent first-order terminal elimination half-life will be calculated as 0.693/Kel.
CL/F:	Apparent total clearance after oral (extravascular) administration, calculated as Dose/AUC0-inf (parent only).
Vz/F:	Apparent volume of distribution during the terminal elimination phase after oral (extravascular) administration, calculated as Dose/(AUC0-inf x Kel) (parent only).

No value for Kel, AUC0-inf, AUC%extrap, CL/F, Vz/F, or t½ will be reported for cases that do not exhibit a terminal log-linear phase in the concentration-time profile.

No PK parameters will be calculated for subjects with 2 or fewer consecutive time points with detectable concentrations, or who have an AE of vomiting that occurs at or before 2 times the median Tmax.

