13.3.5 Urine Pharmacokinetic Parameters

PK parameters for urine TRA will be calculated as follows:

Ae(u):	Amount of TRA excreted in urine within a given collection interval.
CumAe(u):	Cumulative amount of TRA excreted in urine.
%Dose(u):	Percent of administered radioactive dose excreted in urine within a given collection interval.
Cum%Dose(u):	Cumulative percent of administered radioactive dose recovered in urine.
CLr:	Renal clearance. CLr = CumAe(u)/AUC0-inf, where both CumAe and AUC are determined over matched time interval.

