13.3.7 Fecal Pharmacokinetic Parameters

PK parameters for feces TRA will be calculated as follows:

Ae(f):	Amount of TRA excreted in feces within a given collection interval.
CumAe(f):	Cumulative amount of TRA excreted in feces.

%Dose(f): Percent of administered radioactive dose excreted in feces within a given collection interval.

Cum%Dose(f): Cumulative percent of administered radioactive dose recovered in feces.

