14.3.1.3 Metabolite Profiling

CT1812 metabolite profiling will be performed on plasma, urine, and fecal samples containing sufficient amounts of radioactivity. The percent of dose represented by each of the metabolites, if any, will be calculated using the radioactive concentration equivalent data combined with the metabolite profiling data. The percentage of each identified metabolite, if any, to TRA in the plasma will be estimated based on plasma metabolite profiling data. Metabolites accounting for more than 10% of circulating TRA will be identified.

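### Does the silence on predose radioactivity leave percent of dose, mass balance and the TRA pharmacokinetics open to bias?

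*Protocol*

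**What the plan says.** The flow chart (Protocol Section 6) schedules predose samples for whole blood TRA, plasma TRA, urine and feces. Section 13.3.1 says of the blood samples: "Predose samples should be handled, processed, analyzed, and stored separately away from the postdose samples to avoid cross contamination". Sections 13.3.4 and 13.3.6 repeat this for urine and feces. How the predose results enter a calculation is not stated.

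The excretion endpoints are defined in Section 13.3.5 ("Percent of administered radioactive dose excreted in urine within a given collection interval") and Section 13.3.7 ("Percent of administered radioactive dose excreted in feces within a given collection interval"). Section 14.3.1.2 adds them up as the "percent of the TRA recovered in urine and feces relative to the administered radioactive dose minus any radioactive dose lost due to emesis".

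Section 13.3.2 applies to whole blood and plasma TRA as well as to CT1812 and M6. AUC0-last runs "from time 0 to the last observed non-zero concentration". Kel is fitted "using the maximum number of points in the terminal log-linear phase (e.g., three or more non-zero concentrations"), and Kel, half-life and AUC0-inf are not reported when the profile has no terminal log-linear phase.

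Two further quantities use plasma TRA: the Synopsis lists "Ratio of plasma CT1812 to TRA", and Section 14.3.1.3 says "Metabolites accounting for more than 10% of circulating TRA will be identified".

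Section 13.3.10 leaves assay specifics to separate documents. Sections 14.3 and 14.3.1.1 leave detailed methodology to a SAP to be written by the contract research organization. The SAP supplied is a bioanalytical plan for plasma CT1812 and M6 (its Sections 1 and 9) and does not deal with TRA.

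**The concern.** The mass-balance formula names emesis and nothing else, so a literal reader could conclude that no other correction is made. If so, ¹⁴C that did not come from this dose would be counted as recovered dose in urine and feces, and would add a roughly constant amount to every plasma TRA value.

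The tail of the curve is where that would show. With a half-life of 11.1 to 14.0 h (the parent's range in Section 8.1.2), 168 h is 12 to 15 half-lives, so the true late signal is tiny and even a small background would dominate it. Whether a late value is non-zero then depends on whether the baseline was removed first. An inflated TRA AUC would lower the CT1812-to-TRA ratio and could bring a metabolite's share below the 10% identification threshold.

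A raised baseline is possible, because exclusion criterion 18 admits subjects with up to three earlier radiolabeled studies in the preceding 3 to 12 months. No rule says what to do with such a subject. Excretion and blood and plasma TRA are primary endpoints (Section 9), and only 8 subjects are enrolled, with complete data wanted from 6.

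**Working it through.** The documents give no figure to reproduce: the sample size has no statistical basis (Section 14.1) and no background level is stated. Every background level below is an assumption.

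**Recovery**
- Dose: about 1 µCi = 1000 nCi. One percentage point is 0.01 × 1000 = 10 nCi.
- Spread over 168 h (7 days): 10 / 7 = 1.43 nCi/day of uncorrected activity for one point in one subject.
- Effect of that one subject on the mean: 1/8 = 0.13 points, or 1/6 = 0.17 points.
- Carry-over example, with all inputs assumed (earlier 1 µCi dose, 10% in a slow pool, pool half-life 60 days, 90-day gap): 100 × 0.1 × 2^(−90/60) × (1 − 2^(−7/60)) = 0.27 points in that subject, or 0.27/8 = 0.03 to 0.27/6 = 0.05 points in the mean.

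**Plasma TRA**
- Model: one-compartment oral curve scaled to Cmax = 1, assumed absorption rate 3/h (Tmax 1.3 to 1.4 h; Section 8.1.2 gives 60 to 90 minutes), the 18 sampling times in SAP Section 1, linear trapezoid, and a constant background b as a fraction of Cmax.
- True AUC0-168: 17.69 (half-life 11.1 h) and 21.99 (14.0 h).
- AUC increase = b × T / true AUC0-T. At b = 1% and T = 168 h: 1.68/17.69 = 9.5% and 1.68/21.99 = 7.6%. The CT1812-to-TRA ratio is multiplied by 1/1.095 = 0.913 and 1/1.076 = 0.929.

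| b = 1% of Cmax | True t½ 11.1 h | True t½ 14.0 h |
|---|---|---|
| AUC0-24 | +1.8% | +1.6% |
| AUC0-48 | +2.9% | +2.4% |
| AUC0-72 | +4.1% | +3.4% |
| AUC0-168 | +9.5% | +7.6% |
| t½ fitted to 120, 144, 168 h | 586 h | 148 h |
| t½ fitted to 12–48 h | 11.9 h | 14.6 h |

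- At b = 0.1%, AUC0-168 rises by 0.95% and 0.76%, and the 120–168 h fit reads 74 and 30 h.
- If TRA instead declines with an assumed half-life of 60 h, b = 1% adds 2.2% to AUC0-168 and the 120–168 h fit reads 63 h.

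**Which points count for Kel**
At b = 1% and half-life 11.1 h, the values at 120, 144 and 168 h are 1.06%, 1.01% and 1.00% of Cmax. That is a plateau at the subject's own predose level, not a log-linear decline (R² of the log-linear fit is 0.88). Section 13.3.2 restricts Kel to the log-linear phase and withholds it where there is none.

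**The 10% threshold**
A share of 11% reads 10% when the AUC rises by 10%, since 11/1.10 = 10. That needs b = 0.10 × 17.69/168 = 1.05% or 0.10 × 21.99/168 = 1.31% of Cmax (4.5% if the half-life is 60 h), with the full 0–168 h TRA as denominator. Section 14.3.1.3 estimates the share from profiling data, on samples with enough radioactivity. That need not include the late samples that produce the effect.

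**The case for a change.** The best argument for a change is that a subtraction rule is part of the endpoint's definition and not mere assay detail. The protocol already states the emesis adjustment and the vomiting exclusion at this level, so a baseline rule would sit naturally beside them. Writing it down in advance would also prevent a decision about a raised predose value after the results are seen. It would cost a sentence or a citation.

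Part of this stands. The supplied documents do not state the step, and Section 13.3.2 leaves some judgement over which late points are log-linear. A pointer to the TRA analytical document would be harmless.

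The rest does not carry. Section 14.3 requires a protocol amendment for major modifications of a primary endpoint, and removing ¹⁴C that was never administered modifies nothing: Sections 13.3.5 and 13.3.7 already confine the numerator to the administered dose. The analysis population in Section 14.2 gives its criteria as examples, so a raised baseline can be handled there.

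A fixed subtraction rule would also have weaknesses. One spot urine or one stool gives a concentration, not an excretion rate, so subtracting it from every interval can over- or under-correct. Under Section 13.3.6 a predose stool may not exist. Reporting with and without flagged subjects would cure neither problem.

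**Conclusion.** No change is needed. The silence is real, but no stated rule is shown to give a wrong result, and the effect is nil if the baseline is subtracted or negligible. The endpoint definition points analysts to the right treatment, and the baseline data they need are collected.

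Recovery is insensitive: 1.43 nCi/day for a week moves one subject by one point and the mean by 0.13 to 0.17. TRA AUC and half-life could be affected more, but only if no correction is made, the background is near an assumed 1% of Cmax, TRA falls as fast as the parent, the full 168 h interval is used (for AUC) and a plateau is read as a terminal phase (for half-life). Relax these and the errors shrink to 1.6–1.8% for AUC0-24 and less than 1 h for half-life.

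The conclusion assumes that the TRA laboratory or the analyst nets out the predose value, or finds it negligible. The separate TRA documents and the contract research organization's SAP were not available to confirm this.

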8.2 Rationale

8.2.1 Rationale for this Study and Study Design

The disposition of any drug in the body is controlled by physiological processes affecting absorption, metabolism, and excretion. The most efficient and well-established approach to elucidate these processes is a mass balance study in which the drug dose is administered in radiolabeled form, followed by collection and analysis of different biological matrices for radioactivity using liquid scintillation count and determination of drug concentration using conventional liquid chromatography-tandem mass spectrometry and metabolite profile using liquid chromatography with radiometric detection. The PK, metabolic pathways, and routes of elimination of CT1812 have been evaluated in vitro and in vivo in preclinical species (IB, Version 5.0). In this study the TRA of [¹⁴C]-CT1812 will be measured using accelerator mass spectrometry (AMS).

Additionally, the PK profile of CT1812 in humans has been evaluated in healthy subjects (in a SAD and MAD investigation [Study COG0101]). Currently, the biotransformation/metabolism and excretory pathways of CT1812 in humans are not known.

The aim of this study is to characterize the plasma exposure, clearance pathways, and excretion routes for CT1812 and its metabolites in healthy male subjects following oral administration. Based on data in healthy subjects, the average t_{1/2} of CT1812 following single oral administration in the fasted state for doses from 10 mg to 1120 mg (Study COG0101) ranged from 11.1 to 14 hours, thus, it is expected that more than 90% of the radioactivity should be eliminated within 168 hours postdose, the sampling duration in this study.

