13.3.8 Emesis

Collection containers (pre-weighed) for emesis will be available for subjects participating in the study at all times following dosing until discharge from the clinic. Subjects will be instructed at the beginning of the study that they should use one of the designated containers if emesis occurs following [¹⁴C]-CT1812 dosing. If emesis occurs following [¹⁴C]-CT1812 dosing and the subject has been able to collect the emesis in the designated container, it will be weighed and recorded, labeled with subject identification, time, and date, and analyzed for TRA. The subject may continue the study with permission from the Sponsor; however, subject data will be excluded from the PK or mass balance calculations if the AE of vomiting occurs at or before 2 times the median Tmax.

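### Does emesis handling leave the mass balance ill-defined, given that the urine and feces percentages use another denominator and uncollected emesis has no rule?

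*Protocol*

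**What the plan says.** The Synopsis and Section 14.3.1.2 define the total in the same words: "Mass balance will be calculated as a sum of the percent of the TRA recovered in urine and feces", taken "relative to the administered radioactive dose minus any radioactive dose lost due to emesis (if any occurred".

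The route percentages carry no emesis term. Section 13.3.5 has "Cumulative percent of administered radioactive dose recovered in urine" and Section 13.3.7 has "Cumulative percent of administered radioactive dose recovered in feces".

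Section 13.3.8 provides for weighing and assaying emesis if "the subject has been able to collect the emesis in the designated container". It lets the subject continue with the Sponsor's agreement, but sets an exclusion window of twice the median Tmax: "subject data will be excluded from the PK or mass balance calculations if the AE of vomiting occurs at or before 2 times". Section 13.3.2 has a matching rule that no PK parameters are calculated for subjects "who have an AE of vomiting that occurs at or before 2 times the median Tmax".

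Three other places bear on the point:

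- Section 14.2 admits to the PK population only subjects with an evaluable profile, and gives having the measurements as one example of what that requires.
- Section 14.3 assigns detailed methods to a SAP to be prepared by the clinical CRO.
- Section 14.3.1.1 lists emesis radioactivity, where there is any, among the quantities to be summarised.

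The SAP supplied is the bioanalytical laboratory's plan for plasma CT1812 and M6. It does not deal with emesis or mass balance.

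**The concern.** Routes of elimination and overall mass balance are the first primary objective, and Section 9 reports total recovery together with the urine and feces percentages. Suppose a subject vomits after the exclusion window, is kept, and has measured emesis radioactivity. The table would then show two route percentages on one denominator and a total on another, and a reader adding them would find a discrepancy. The sentence in Section 14.3.1.2 can also be parsed as subtracting the emesis loss from the recovered percentage, which gives a quite different number.

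If the late emesis was not collected, there is nothing to subtract and that subject's recovery reads low. This could be mistaken for incomplete excretion, since Section 8.2.1 says "it is expected that more than 90% of the radioactivity should be eliminated within 168 hours postdose". Vomiting is among the adverse events listed in Section 8.1.2, and with 8 subjects enrolled to obtain 6 complete, a single subject carries weight in the mean.

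**Working it through.** The documents give no figure for emesis or mass balance, so there is nothing to reproduce. The check measures how far the definitions can diverge.

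**Inputs.** r = fraction of the retained dose recovered in urine plus feces, set at 0.90 for illustration (Section 8.2.1 expects more than this). e = fraction of the dose vomited and c = fraction of the emesis collected; both are assumptions. Number of subjects: 8 enrolled, 6 complete (Section 14.1).

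**Step 1: the two denominators, all emesis collected.**
- Sum of route percentages on administered dose = 100 × r × (1 − e)
- Mass balance on net dose = 100 × r × (1 − e)/(1 − e) = 100 × r
- Gap = 100 × r × e

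| e (assumed) | Urine + feces, administered dose | Mass balance, net dose | Gap (points) | Gap/8 | Gap/6 |
|---|---|---|---|---|---|
| 0 | 90.0 | 90.0 | 0 | 0 | 0 |
| 1% | 89.1 | 90.0 | 0.9 | 0.11 | 0.15 |
| 2% | 88.2 | 90.0 | 1.8 | 0.23 | 0.30 |
| 5% | 85.5 | 90.0 | 4.5 | 0.56 | 0.75 |
| 10% | 81.0 | 90.0 | 9.0 | 1.13 | 1.50 |

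**Step 2: can the reader convert?** Yes. With e = emesis radioactivity / administered radioactivity, net-dose recovery is the administered-dose sum divided by (1 − e). At e = 10% this is 81.0/0.90 = 90.0. The cumulative amounts in urine and feces (Sections 13.3.5 and 13.3.7) and the emesis radioactivity (Section 14.3.1.1) are all to be summarised, so no information is lost.

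**Step 3: the other parsing.** Subtracting the loss from recovery gives 81.0 − 10 = 71.0 at e = 10%. This counts the vomited dose against the subject twice: once because it never reached urine or feces, and again as a deduction. An analyst would not choose that reading; net dose is the natural one.

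**Step 4: incomplete collection.** Mass balance = 100 × r × (1 − e)/(1 − c × e). At e = 10%: 90.0 if all is collected, 81.0/0.95 = 85.3 if half is, 81.0 if none is. The bias is real for that subject, but no choice of denominator removes it, because the loss was never measured.

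**Step 5: who is exposed.** Single-dose Tmax was 60 to 90 minutes (Section 8.1.2), so twice Tmax is about 2 to 3 hours. Vomiting before that removes the subject whether or not the emesis was collected. Only later vomiting counts, and by then less of an oral dose would be expected to remain in the stomach, though the documents do not quantify this.

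**Step 6: how often.** No rate is given. If a fraction p of subjects vomited late, the chance of at least one among 8 is 1 − (1 − p)^8: 15%, 34% and 57% for assumed p of 2%, 5% and 10%. That is the chance of any late vomiting. If one episode in five went uncollected (also assumed), p becomes 0.4%, 1% and 2%, and the chance falls to 3%, 8% and 15%.

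**The case for a change.** The best argument for a change is that it costs only wording and concerns a primary endpoint. A formula for that endpoint should not depend on how a sentence is parsed. Section 14.3 itself requires an amendment for major changes to the primary endpoint definition, which favours settling it before data are seen. Containers are kept available until discharge, so late vomiting is foreseen, and the SAP supplied does not fill the gap. Nor do Sections 13.3.2 and 13.3.8 say which analyte's median Tmax sets the window, although Tmax is calculated for whole-blood and plasma radioactivity, CT1812 and M6.

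All of this is accurate as a reading of the text. What stands is that one sentence could be tighter, one contingency is unwritten and one analyte is unnamed. What does not stand is the claim of harm:

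- The denominators are labelled in the definitions, so the mismatch is one of presentation and not a bias.
- A subject with an unmeasured loss is not kept automatically. Continuing needs the Sponsor's agreement (Section 13.3.8), the PK population turns on evaluability (Section 14.2), and replacement is possible (Sections 10.1 and 12.3).
- Subjects are confined through 168 hours with containers to hand, and adverse events are recorded with onset time and listed by subject (Sections 13.2.8.3 and 14.3.2). An affected subject would be visible in the report.
- The 90% in Section 8.2.1 supports the length of sampling. The study is descriptive, with no recovery threshold for a subject to fail.
- The clinical CRO's SAP was not supplied, so absence of a rule is shown only for these two documents.

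**Conclusion.** No change to the plan follows. The wording differs between Sections 13.3.5 and 13.3.7 on one side and Section 14.3.1.2 and the Synopsis on the other, and missed late emesis has no written rule. These are details that an analyst fills sensibly: compute the total on net dose, label the denominators, and footnote any subject whose emesis was not collected.

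The effect is zero unless a retained subject vomits after roughly 2 to 3 hours, a window that assumes Tmax as in the earlier single-dose data. If one does, the subject's gap is r × e. At r = 0.90 and e of 1% to 10% that is 0.9 to 9.0 points for the subject, and 0.11 to 1.13 points on a mean of 8. With collected emesis this is a difference between two labelled quantities that convert exactly. With uncollected emesis it is a downward bias in one subject's recovery, which rewording cannot repair. The values of e, c and p are assumptions throughout, and r = 0.90 is illustrative.
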